6.1 Screening population

The "Screening population" (SCR) is defined as all subjects will sign the informed consent.

6.2 ENROLLED ANALYSIS POPULATION

The "Enrolled population" (ENR) is defined as all subject who will be enrolled in the study. Subjects who signed the informed consent but do not satisfy the eligible criteria should be withdrawn from the study prior to implant and will be considered as screening failure.

Screening failures will be reordered into logs that are supplied to the sites. These logs can be collected by monitors for internal sponsor records and screen failures will be not entered into e-CRF.

All enrolled subjects will be analyzed under the Intention-To-Treat (ITT) principle, such that subjects will be analyzed according to the final implant attempt to place an aortic Perceval valve. The ENR will be used mainly for subject disposition summaries.

6.3 SAFETY ANALYSIS POPULATION

The "Safety" population (SAF) is defined as all enrolled subjects successfully implanted with one of the study aortic heart valves. The SAF population will coincide with the ENR population and will be used for efficacy, performance and safety summaries.

6.4 Per-Protocol Population

Per-Protocol" population (PP) is defined as all subject in the SAF without the major primary endpoint-related protocol deviations as defined and reported in the latest version of the study Risk Based Study Management Plan.

The PP population will be used for the sensitivity analysis on primary endpoint.

6.5 Usage of analysis populations

Table 1: Use of analysis sets

	ENR	SAF	PP
Subject disposition	Х	Х	Х
Discontinuations		Х	
Protocol deviations		Χ	
Subject demographics		Х	
Implant characteristics		Χ	
Other baseline characteristics		Х	
Medical history		Χ	
Prior cardiovascular procedures		Χ	
Concomitant procedures		Χ	
Prior and concomitant medication		Χ	
Compliance		Χ	
Primary analyses		Χ	X
Secondary efficacy analyses		Χ	
Secondary performance analyses		Χ	
Safety		Х	

7 DISPOSITION

7.1 SUBJECT DISPOSITION

For describing the subject disposition, the following populations will be summarized overall and for the subgroups defined in Section 5.3.

Study: APR002 BELIEVE

- Subject signed the informed consent and enrolled (only overall)
- Subjects in the SAF
- Subjects in the PP
 - Reasons for PP exclusion
- Implant procedure completers
- Study completers

For subject in the SAF the percentage denominator will be the number of subject signed the informed consent and enrolled (ENR). For all other calculations, the percentage denominator will be the number of subject in the SAF.

COPYRIGHT LIVANOVA. ALL RIGHTS RESERVED. MAY NOT BE REPRODUCED WITHOUT PERMISSION. ALL HARD COPIES SHOULD BE CHECKED AGAINST THE CURRENT ELECTRONIC VERSION WITHIN MASTERCONTROL PRIOR TO USE AND DESTROYED PROMPTLY THEREAFTER. ALL HARD COPIES ARE CONSIDERED UNCONTROLLED DOCUMENTS.

LN-GLB-CLN-TEM-0033 rev1 Page 13 of 42

7.2 SUBJECT DISCONTINUATION

Number and percentage of discontinuations will be presented for subjects in the SAF. Reasons for study termination (e-CRF section "Study Termination") will be presented and percentage denominator will be the number of subjects discontinuing. The details for "other reasons" will be presented in a listing, if applicable.

Study: APR002 BELIEVE

The distribution of the time to study termination will be summarized using time-to-event methods. The starting date of the time to study termination will be from the implant (study day 1). Time will be months until termination. The time to study termination will be censored at the date of study termination or analysis cut-off date, if applicable.

If more than 20% of enrolled subjects terminate the study due to Serious Adverse Events (SAEs) other than leading to death, time to withdrawal due to SAEs will be calculated and evaluated as described above only for subjects who discontinued due to SAEs.

All data will be presented in a subject data listing sorted by subject ID.

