8.2. HANDLING OF STUDY DISCONTINUATIONS

8.2.1. Handling of Subject Temporary Treatment Discontinuation or Termination

For all subjects reaching the end of the study (completed 1 year visit, death, or explants) or in case of premature withdrawal as described in Section 6.3.5 (lost-to-follow-up, or subject's decision) a study termination form will be filled out in order to document the date and reason for discontinuation.

Every attempt must be made to have all subjects complete the follow-up visit schedule. A subject will be considered lost to follow-up when all efforts to obtain information are unsuccessful. At a minimum, the effort to obtain information must include at least two (2) attempts to make contact via phone, and a certified letter should be sent to the subject's last known address. Both phone contacts and copy of the letter must be documented/available in the subject's medical record and recorded in the eCRF. For subjects discontinued by the PI for a safety reason, the PI shall document the reasons for the decision.

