18.13 DATA DERIVATIONS

Derived variable	Derivation algorithm based on e-CRF version 8 dated 18 th July 2017
Concomitant	"Implant Surgical Details" e-CRF:
Procedures	Group "Implanted with a concomitant procedure" if CPYN= "Yes"
	Group "Implanted without a concomitant procedure" if CPYN= "No"
Subject symptoms	"Subject Clinical Assessment" e-CRF at "at 1 Month After ACT Dx (1st CT-Scan)" or "Reduced Leaflet Visit (2nd CT-Scan)" Visits:
	Group "Asymptomatic" if SCSYMPYN = "No"
	Group "Symptomatic" if SCSYMPYN = "Yes"
ACT/DATP	"Subject Clinical Assessment" and e-CRF:
	 Group "Subject on ACT/DAPT at hospital discharged (or 30-days after implant)" if SCDISCYN= "Yes"
	Group "Subject off ACT/DAPT at hospital discharged (or 30-days after implant" if SCDISCYN= "No"
Core Lab evaluation	"Vist (at 1 Month After ACT Dx or at Reduced Leaflet)" e-CRF:
by	Group "CT scan" if IMGTYPE= "4D CT Acquisition"
	Group "TEE" if IMGTYPE = "Transesophageal Echo"
Pre-implant period	If Enrolled Date= DXSTDAT2 ("Implant Surgical Details" e-CRF) then
	Start date: ICFDAT ("Inclusion/Exclusion Criteria" e-CRF)
	End date: DXSTDAT2 -1
	If Enrolled Date= ICFDAT then
	Start date=End date= "None".

LN-GLB-CLN-TEM-0033 rev1 Page 39 of 42

Post-implant period	If DXPER= "Yes" ("Implant Surgical Details" e-CRF) Start date: DXSTDAT2, End date: if SCDISCYN= "No" ("Subject Clinical Assessment" e-CRF) then End date= VISDAT (at Hospital Discharge visit) + 30 if SCDISCYN= "Yes" ("Subject Clinical Assessment" e-CRF) then End date= VISDAT (et ACT Disceptionation visit) + 30
Post-ACT/DAPT period	 End date= VISDAT (at ACT Discontinuation visit) + 30 Start date: if SCDISCYN= "No" ("Subject Clinical Assessment" e-CRF) then Start date= VISDAT (at Hospital Discharge visit) + 31 if SCDISCYN= "Yes" ("Subject Clinical Assessment" e-CRF) then Start date= VISDAT (at ACT Discontinuation visit) + 31 End date: VISDAT (at Year 1 visit)
Implant procedure completer	 DXPERF= "Yes" ("Implant Surgical Details" e-CRF) and DSSTDAT ≥ ACTDIDAT ("Study Termination" e-CRF) + 31 o if DSSTDAT missing, last available VISDAT ≥ ACTDIDAT + 31
Study completer	DSDECOD= "Completed" ("Study Termination" e-CRF)
SCR population	ICFDAT not missing ("Inclusion/Exclusion Criteria" e-CRF)
Enrolled Date	Derived from maximum between Consent Date and Implant Date. "Inclusion/Exclusion Criteria" e-CRF and "Implant Surgical Details" e-CRF Max(ICFDAT; DXSTDAT2)

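### SAP 7.2 censors time to study termination at the termination date and defines no event, and it limits time to SAE withdrawal to those who withdrew; only these supplementary disposition curves are affected

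*SAP*

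**What the plan says.** SAP 7.2 announces the method: "The distribution of the time to study termination will be summarized using time-to-event methods". Time runs from implant, in months. The censoring rule follows: "The time to study termination will be censored at the date of study termination or analysis cut-off date, if applicable". The section does not say which terminations are events.

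A conditional analysis comes next. Its trigger is: "If more than 20% of enrolled subjects terminate the study due to Serious Adverse Events (SAEs) other than leading to death". When it is met, "time to withdrawal due to SAEs will be calculated and evaluated as described above only for subjects who discontinued due to SAEs".

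The same section also provides simple counts: "Number and percentage of discontinuations will be presented for subjects in the SAF". Reasons for termination are tabulated among those discontinuing, and all the data are listed by subject.

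Three other places bear on the curve.

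- SAP 18.13 derives time to study termination as [DSSTDAT – DXSTDAT2 + 1] / 30.4375, with no event flag and no restriction by reason. It identifies a study completer by DSDECOD equal to Completed on the Study Termination form.
- Protocol 8.2.1 covers subjects who complete the 1-year visit, die or are explanted, as well as those who withdraw early. For all of them, "a study termination form will be filled out in order to document the date and reason for discontinuation".
- SAP 5.2 and the time-to-event row of SAP 18.13 censor ongoing event-free subjects at the analysis cut-off, and subjects who discontinue without an event at discontinuation.

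**The concern.** A time-to-event analysis needs a rule saying who has the event and who is censored. Here the date of the event being timed is given as a censoring date, so a programmer following the text has nothing to count. The general rule in SAP 5.2 does not help: it covers people who discontinue without the event, and here discontinuation is the event.

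The natural repair, treating the termination date as the event date, is also unsafe, because that date exists for completers as well. By the final analysis, which follows all the 1-year visits, nearly every subject should have one.

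The SAE-withdrawal analysis has a different fault. A risk set made up only of people who had the event must end at zero, so the height of the curve says nothing about how common the event was.

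At stake is the only planned curve of when subjects leave the study. Without a usable one, a reader would have to rebuild the timing from the listing.

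**Working it through.** **The plan's only related figure.** SAP 7.2 states no computed figure. The nearest is the enrolment target in SAP 2.3: 75 evaluable scans with 15% attrition gives 75 / (1 − 0.15) = 88.2, so approximately 88 reproduces. That 15% is an allowance for missing evaluable scans. It is not a 1-year termination rate.

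**Illustration for time to termination.** Assume 88 subjects, of whom 13 terminate early (88 × 0.15 = 13.2, borrowing the scan allowance purely as an example). The other 75 complete, and nobody is censored before the last early termination. The Kaplan-Meier estimate after d events is then 1 − d/N.

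| Reading of the rule | Events | Kaplan-Meier at the end |
|---|---|---|
| Literal: termination date is a censoring date | 0 | 1.00 (0% stopped) |
| Every DSSTDAT is an event | 88 | 0 at the 1-year visits (100% stopped) |
| Premature termination is the event, completers censored | 13 | 1 − 13/88 = 0.852 (14.8% stopped) |

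The first row does not depend on the number stopping: it is 1.00 for 0, 13 or 88. The second reaches 0 whatever the number, because completers count too. Only the third responds to early stopping.

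**Illustration for SAE withdrawal.** The trigger is more than 0.20 × 88 = 17.6 subjects, so at least 18. Take 18 withdrawals and no other losses.

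- After the 9th withdrawal, withdrawers only: 1 − 9/18 = 0.50. All 88 at risk: 1 − 9/88 = 0.898.
- After the 18th, withdrawers only: 1 − 18/18 = 0. All 88 at risk: 1 − 18/88 = 0.795, or 20.5% withdrawn.
- With 30 or 60 withdrawals the restricted curve still ends at 0. The full-population curve would end at 1 − 30/88 = 0.659 or 1 − 60/88 = 0.318.

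The steps of the restricted curve do mark when the withdrawers left; only its height is uninformative. If the phrase referring back to the description above also carries over the censoring sentence, this analysis has no events either and stays at 1.00.

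**The case against.** The strongest reply is that little depends on these curves. SAP 7.2 separately reports how many discontinued, what percentage and why, with a listing. SAP 7.1 counts study completers, SAP 9 gives compliance by visit, and SAP 18.5 requires observed and missing counts at each visit to add up. The study is descriptive, and neither the primary estimate nor its interval uses the curves. All of this stands, and it is why the point is minor.

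It can also be said that the censoring sentence, with its closing qualifier, was meant for completers and ongoing subjects, and that the completer flag already exists. That is plausible. But the sentence does not say so, and neither SAP 7.2 nor the derivation in SAP 18.13 links the flag to the curve. The remedy is the same either way: define the event.

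A reader might infer more than the documents support.

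- *That loss of subjects would be hidden, or could not be judged before the first CT.* The separate counts, reasons, listing and visit-level tables contradict this.
- *That the SAE-withdrawal curve shows neither how many nor when.* It shows timing among withdrawers, unless the censoring sentence carries over to it.
- *That the SAE-withdrawal analysis will be run.* It depends on the 20% trigger. Eighteen non-fatal SAE terminations is more than the 13 subjects the plan allows for all scan attrition.
- *That the correct 1-year termination estimate is about 15%.* Subjects unable to stop anticoagulation or dual antiplatelet therapy stay in the study to 1 year (Protocol 7.5), scans can be unreadable, and subjects can leave after the first CT. The two rates need not agree.

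**Conclusion.** The point holds, at minor severity. SAP 7.2 names the termination date as a censoring date and defines no event, and no other section repairs this. Depending on an unstated programming choice, the illustrative study would show 0%, 14.8% or 100% terminated at 1 year. The two extremes follow from the rules themselves; the middle figure rests on the assumed 13 early terminations among 88. What is established is a missing event definition, not a certain loss of all events.

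The SAE-withdrawal analysis, if triggered, can describe timing among withdrawers but cannot estimate risk in the SAF. With the minimum 18 withdrawals it ends at 0, where the full-population estimate would be 0.795, assuming no other losses.

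The consequences stop at these two supplementary disposition curves.

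**What to change.** In SAP 7.2 and the matching row of SAP 18.13:

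1. Define the event as premature study termination, meaning DSDECOD other than Completed. State how death is handled, and do the same for explant, since Protocol 8.2.1 groups both with reaching the end of the study.
2. Censor completers at their 1-year visit or termination date, and ongoing subjects at the analysis cut-off, in line with SAP 5.2.
3. If the 20% trigger is met, run time to SAE withdrawal in the whole SAF, with withdrawal for a non-fatal SAE as the event and other terminations either censored or treated as competing events. State which.
4. Label any expected 1-year termination figure, such as 15%, as an illustrative assumption.

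The cost is a few lines of SAP text and one derived flag. DSDECOD, DSSTDAT and the implant date are already collected, so no new data are needed.

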7.3 PROTOCOL DEVIATIONS

Major primary endpoint-related (PER) and major other protocol deviations will be summarized overall based on the SAF population.

Protocol deviations will be classified as collected in the "Protocol Deviation" e-CRF or in Section 6.4. Major protocol deviations will be presented in a subject data listing sorted by site, type (PER and other) and subject ID. Minor protocol deviations will be presented in a separate listing also sorted by site and subject ID.

8 DEMOGRAPHICS AND OTHER BASELINE CHARACTERISTICS

Subject demographics and baseline characteristics will be summarized descriptively overall.

8.1 SUBJECT DEMOGRAPHICS

The demographics characteristics will be analyzed by means of summary statistics, as appropriate, for the SAF.

Subject demographics are age [year], age group [<18 years (if applicable), ≥18 years and <65 years, ≥65 years and <85 years, and ≥85 years], gender, race, and ethnicity.

8.2 IMPLANT CHARACTERISTICS

The following implant characteristics will be analyzed by means of summary statistics in the SAF: successful implant, labeled valve size, surgical approach, abnormality of ascending aorta (and specifications), availability of condition of aortic leaflets (and specifications), abnormality of aortic root (and specifications), post-operative cardiac rhythm.

8.3 OTHER BASELINE CHARACTERISTICS

For parameters collected on more than one occasion during the study including baseline, the assessment at baseline will be presented with assessments collected later on in the study and not in a separate table. These parameters are:

Study: APR002 BELIEVE

- Subject clinical assessment: NYHA classification, infections, cardiac rhythm, ACT/DAPT status and medication change/discontinuation, aortic valve dysfunction symptoms.
- Vital signs: height [m] (only at prior to implant/implant visit), weight [kg], body mass index (BMI) [kg/m²], body surface area (BSA) [m²], systolic blood pressure (SBP) [mmHg], diastolic blood pressure (DBP) [mmHg], and presence of congestive heart failure.
- Hemodynamic performance thought transthoracic echocardiogram (TTE).

The other remaining characteristics at implant will be summarized descriptively, as appropriate: concomitant procedures, intraoperative TEE, cardiac rhythm at implant. Details on complications of concomitant procedures will be listed by subject ID, if applicable.

8.4 Medical History and Previous Cardiovascular Procedures

Medical history will be analyzed by means of summary statistics. It includes but it is not limited to history of systemic hypertension, coronary artery disease, angina, myocardial infarction, heart failure, carotid artery disease previous carotid artery intervention or percutaneous transluminal carotid angioplasty (PTCA), transient ischemic attack (TIA), stroke, endocarditis, peripheral vascular disease, pulmonary hypertension, chronic lung disease, diabetes, dyslipidemia, neoplasia, tobacco user.

Previous cardiovascular procedures will be summarized descriptively, as appropriate: coronary artery bypass surgery (CABG) and specifications, percutaneous coronary intervention, arrhythmia procedure and specifications, pulse generator implant and specifications, revision of the Aortic Valve Replacement Surgery and specification, STS predicted risk of mortality [%], where applicable. Details for "other arrhythmia procedure" and year of intervention/implants will be presented in a listing, if applicable.

8.5 Prior and concomitant medications

Prior and concomitant medications will be collected in the "Medication" e-CRF as per enrollment. For the analysis, the following algorithm will be used to define prior and concomitant medication:

- Prior will be any medication stopped prior to study day 1, regardless of its start date.
- Concomitant will be any medication not stopped before study day 1, regardless of its start date or medication started after study day 1.

These will be summarized by number and percentage of subject receiving them and sorted alphabetically separately for prior and concomitant medications by a predefined list of medication type in "Medications" e-CRF.

Bar plot of the medication type will be created showing the percentage distributions.

COPYRIGHT LIVANOVA. ALL RIGHTS RESERVED. MAY NOT BE REPRODUCED WITHOUT PERMISSION. ALL HARD COPIES SHOULD BE CHECKED AGAINST THE CURRENT ELECTRONIC VERSION WITHIN MASTERCONTROL PRIOR TO USE AND DESTROYED PROMPTLY THEREAFTER. ALL HARD COPIES ARE CONSIDERED UNCONTROLLED DOCUMENTS.

9 COMPLIANCE

Compliance will be calculated, for subjects in the SAF, at each follow-up study visit by using the following approach:

Study: APR002 BELIEVE

Compliance at V_i [%] = [1-(number of assessments not done or out of window at Vi / expected number of assessments performed at V_i)] x 100,

where V_i represent the current visit for i=1,...,K and K=3 is the maximum number of follow-up visit could be performed by a subject (Section 5.4).

The number of expected assessments performed at V_i will be calculated as the sum of number of assessments performed and number of assessments not done or out of window, for subject still active in the study at V_i .

An assessment at V_i will be considered as "performed" if a complete visit date is available in the corresponding e-CRF and at least one information is entered.

An assessment at V_i will be considered as "not done or out of window" if a visit-specific protocol deviation will be marked as "Visit/Follow-up Not Done" or "Visit/Follow-up Out of Window" in the corresponding "Protocol Deviation" e-CRF.

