2.3 SAMPLE SIZE CALCULATION

A sufficient number of subjects will be enrolled in this study to allow a minimum of 75 evaluable CT scans for the primary endpoint. Evaluable scans are those where a determination of normal or abnormal leaflet motion is possible. Considering an attrition rate of 15% of subjects, the sample size targeted for enrollment is approximately 88 subjects.

A sample size of 75 evaluable CT scans produces an Exact two-sided 90% CI with a width lower than 13% when the sample proportion is lower than 10% (evaluation calculated using PASS software, version 13).

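### SAP section 9 lets a visit performed out of window count twice in the compliance denominator, so reported visit compliance is too high whenever such visits occur

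*SAP*

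**What the plan says.** SAP section 9 (Compliance) fixes the population and the visits: "Compliance will be calculated, for subjects in the SAF, at each follow-up study visit". The formula is "1-(number of assessments not done or out of window at Vi / expected number of assessments performed at V_i)] x 100".

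The denominator is then defined, among subjects still active at that visit, as the "sum of number of assessments performed and number of assessments not done or out of window".

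Each of the two terms in that sum has its own operational definition in the same section:

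- An assessment is "considered as 'performed' if a complete visit date is available in the corresponding e-CRF and at least one information is entered".
- It is not done or out of window if a visit-specific protocol deviation is "marked as 'Visit/Follow-up Not Done' or 'Visit/Follow-up Out of Window' in the corresponding 'Protocol Deviation' e-CRF".

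The first definition has no timing condition. The second does not exclude visits that already satisfy the first. The derivation table in SAP 18.13 has no compliance entry that would settle the matter.

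**The concern.** A sum of two groups gives an expected total only if no visit belongs to both. Here a visit that took place outside its window, with a date and data recorded, meets both definitions. It would add two to the expected total and one to the count held against compliance, so the denominator would exceed the number of active subjects and the percentage would rise.

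At stake is the accuracy of a table that readers use to judge how well the visit schedule was kept. The error runs in one direction only, and it grows with the number of mistimed visits, so the table would be least reliable where adherence to the windows was poorest.

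**Working it through.** **Inputs**

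- Formula and both definitions: SAP section 9.
- Number of subjects: SAP 2.3 says "the sample size targeted for enrollment is approximately 88 subjects". I use N = 88 for illustration and assume that all are active and due at the visit.
- Numbers out of window and not done: not given in the documents. I assume ND = 5 and let W run from 0 to 30.
- I take one assessment per subject per visit. I also assume that every visit performed out of window carries the deviation flag, and that a visit not done has no date or data.

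The plan states no compliance figure, so there is none to reproduce.

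**Algebra**

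Let I = performed in window, W = performed out of window, ND = not done, and N = I + W + ND.

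1. Performed under the SAP definition: I + W.
2. Not done or out of window: ND + W.
3. SAP denominator: (I + W) + (ND + W) = N + W.
4. SAP compliance: 1 − (ND + W)/(N + W) = (N − ND)/(N + W) = (I + W)/(N + W).
5. Compliance with each visit counted once: 1 − (ND + W)/N = I/N.
6. Excess: (I + W)/(N + W) − I/N = W(N − I)/[N(N + W)] = W(W + ND)/[N(N + W)].

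The excess is zero when W = 0 and positive whenever W > 0. Visits not done cause no error on their own, because they enter the sum once.

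**Numbers (N = 88, ND = 5; W assumed)**

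| W | I | SAP denominator | SAP formula | Each visit once | Excess (points) |
|---|---|---|---|---|---|
| 0 | 83 | 88 | 83/88 = 94.3% | 83/88 = 94.3% | 0 |
| 5 | 78 | 93 | 83/93 = 89.2% | 78/88 = 88.6% | 0.6 |
| 10 | 73 | 98 | 83/98 = 84.7% | 73/88 = 83.0% | 1.7 |
| 20 | 63 | 108 | 83/108 = 76.9% | 63/88 = 71.6% | 5.3 |
| 30 | 53 | 118 | 83/118 = 70.3% | 53/88 = 60.2% | 10.1 |

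As a check on step 6, W = 10 gives 10 × 15/(88 × 98) = 150/8,624 = 1.7 points. The limiting case shows the defect most plainly: if all 88 visits were performed out of window, the SAP formula would give 88/176 = 50% where no visit was compliant.

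**Can W be expected to be zero?** The documents do not say. The SAP provides a deviation category for such visits, so it allows for them. For subjects discharged on ACT/DAPT, the first-CT window is also stated in two ways. The schedule of procedures and SAP 5.4 give 30 days after discontinuation with a 60-day allowance. The visit window guide (Protocol 7.10, SAP 18.6) gives days 60 to 240 from discontinuation. A scan on day 45 is inside one and outside the other, so W at that visit depends on how the two statements are reconciled.

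**The case against.** The strongest reply is that the authors meant a partition. The section calls the denominator an expected number for subjects still active at the visit, and that makes sense only if each subject's visit falls in one group. A programmer might let the deviation flag take precedence, so that performed means performed in window. The denominator would then be N and the formula would be right. This is a fair account of the likely intention, but the text does not say it. Performed is explicitly defined without a timing condition, and nothing elsewhere in the SAP makes the groups exclusive. If a partition was meant, the same short edit is needed to say so.

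A second reply is that the harm is limited. Under SAP 7.3, major deviations are summarised and listed and minor deviations are listed separately, so a reader of the full report could recover the counts of mistimed and missed visits. That stands, but it does not correct the percentage in the table.

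A reader might go further and infer that, because the timing of the first CT is part of the primary endpoint, a distorted compliance figure also distorts the primary result. The documents do not support this. The primary estimate is the proportion with reduced leaflet motion in the safety population, based on the first scan (SAP 10.3 and 10.4). Per-protocol membership depends on major primary-endpoint-related deviations defined in the Risk Based Study Management Plan (SAP 6.4), not on the compliance percentage. Table 1 in SAP 6.5 lists compliance as a summary of its own.

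**Conclusion.** The point holds as a defect in the definitions, with a conditional effect. Followed literally, SAP section 9 overstates visit compliance by W(W + ND)/[N(N + W)]. With N = 88 and ND = 5, that is nothing at W = 0, under 2 points up to W = 10, and about 5 points at W = 20.

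The algebra rests only on the SAP definitions and on mistimed visits being flagged. The sizes rest on assumed counts. It would be wrong to infer that the reported figure is certain to be overstated, since that needs at least one visit performed out of window and a programmer who applies the text as written.

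The consequence is confined to one descriptive table on the safety population. The primary estimate, its 90% CI and the per-protocol set are unchanged, so this is a minor correction.

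**What to change.** Make one of two equivalent changes in SAP section 9:

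- add to the definition of performed that the visit took place within its window; or
- set the denominator to the number of active subjects due at V_i, each counted once (in window + out of window + not done).

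Either gives I/N. The cost is one line of text and no new data. The only downside is that the reported compliance may be slightly less favourable than under the present wording.
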